**STUDY-WIDE RECRUITMENT METHODS: N/A**

## **MULTI-SITE RESEARCH: N/A**

### **STUDY TIMELINES:**

Each enrolled subject will receive a follow up telephone call 24 hours and one week after the procedure. The anticipated duration for study enrollment is 6 months.

### **STUDY ENDPOINTS:**

#### **Primary outcome:**

Change in upper extremity strength defined by dynamometry measurements for each individual in each treatment group before and 30 minutes after the procedure (CESI or no CESI).

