**Non CESI Group (control)**

**Inclusion Criteria:**

All patients ages 18 years or older who will undergo trigger point injections (TPI)

TPI include: Occipital facet or cervical facet injection

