**STUDY-WIDE NUMBER OF PARTICIPANTS:**

Sample Size Calculation

Group 1: n = 60 (CESI with Lidocaine Diluent)

Group 2: n = 60 (CESI with Saline Diluent)

Group 3: n = 20 (no CESI, control group)

A power analysis was performed based upon previous observations of changes in UE strength (24,25) using Fisher's Exact Test. Sample sizes of 52 in each of the two treatment groups will achieve > 80% power to detect a group different in proportions, assuming 20% of patients in the Lidocaine group will demonstrate a motor deficit after the CESI and those in the Saline group will demonstrate no difference in motor strength after the CESI, and further assuming a 2% measurement error with the strength testing method described. The alpha level of this test statistic is set at 0.05, but the significance level actually achieved by this study design is 0.0004. To allow for drop outs, a total of 130 subjects will be enrolled in group 1 and 2. Group 3 will enroll a convenience sample of 20 control subjects based on available patients. Total of 150 subjects for the study will be enrolled.

**Statistical analysis:** The primary outcome (UE strength by dynamometry will be compared between the lidocaine and control group using Fisher's Exact Test. Secondary outcomes will be compared using the Mann-Whitney test for continuous data and a chi-squared statistic. A P <0.05 will be required to reject the null hypothesis.

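### The primary outcome is worded as a change in strength but tested as a proportion with a motor deficit that is never defined; the 2% behind n = 52 and the comparator also need naming

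*Combined protocol and SAP*

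**What the plan says.** All places are in the combined protocol and SAP.

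- **Aims.** Research Question and Null Hypothesis both concern a difference in upper extremity strength between lidocaine and saline as diluent.
- **Outcome.** The Study Endpoints section gives the primary outcome as follows: "Change in upper extremity strength defined by dynamometry measurements for each individual in each treatment group before and 30 minutes after the procedure".
- **Measurements.** Procedures Involved lists handgrip, wrist extension, elbow flexion and elbow extension on both sides, so eight results per patient. There are three readings per test at baseline. The number at 30 minutes is not given.
- **Power.** Sample Size Calculation uses Fisher's exact test with 52 per treatment group for more than 80% power, "assuming 20% of patients in the Lidocaine group will demonstrate a motor deficit after the CESI", no difference in the saline group, and "further assuming a 2% measurement error with the strength testing method described". It adds that "the significance level actually achieved by this study design is 0.0004". Group sizes are listed as 60 and 60, and "a total of 130 subjects will be enrolled in group 1 and 2" to allow for dropout.
- **Analysis.** Statistical analysis: "The primary outcome (UE strength by dynamometry will be compared between the lidocaine and control group using Fisher's Exact Test".
- **Label.** The same section lists "Group 3: n = 20 (no CESI, control group", and the eligibility section heads that group "Non CESI Group (control". The study design also calls Group 3 the control group.

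**The concern.** Fisher's test needs one yes/no result per patient. The outcome section supplies a change on a continuous scale, measured eight times over. Two statisticians following this plan could classify the same patients differently and reach different primary results. If the rule were chosen after seeing results by group, the 0.05 criterion would lose its protection. The size of the change, which is what the aims ask about, is not analysed at all.

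The power statement inherits the gap, because its two rates are properties of a rule that is not written down. The 2% looks like a property of the dynamometer but acts as the saline event rate. Finally, taken at its word, the test sentence compares lidocaine with the group that carries the control label: 20 patients who are neither randomised nor blinded, and who have a different procedure.

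**Working it through.** **Inputs.** From Sample Size Calculation: 52 per arm, 20% on lidocaine, 2%, alpha 0.05, achieved level 0.0004. Sidedness is not stated; two-sided is inferred because it reproduces the figures.

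**Formula.** Power = Σ over x, y of Bin(x; n, p_L) × Bin(y; n, p_S) × [two-sided Fisher p ≤ 0.05]. Achieved size is the same sum with both arms at p_S.

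**Step 1: reproduce the plan.** With p_L = 0.20, p_S = 0.02 and n = 52, power is 0.803 and size is 0.0004. The smallest n reaching 80% is 52, so all the stated figures match. Alternatives do not fit:

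- p_S = 0: power at 52 is 0.963, and 39 per arm would suffice.
- One-sided, 20% v 2%: 43 per arm suffice, and size at 52 is 0.0014.
- Normal approximation, 20% v 2%: 47 per arm without and 57 with continuity correction.

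So the 2% enters as the proportion of saline patients classed as having a deficit.

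**Step 2: dependence on the rule.** Two-sided Fisher power by number analysed per arm. The 60 is the listed group size; 65 is 130/2 and assumes no dropout. The 5% and 15% are assumed alternatives.

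| Lidocaine v saline | 52 | 60 | 65 |
|---|---|---|---|
| 20% v 2% | 80% | 88% | 91% |
| 20% v 5% | 53% | 63% | 68% |
| 15% v 2% | 54% | 64% | 70% |

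**Step 3: why the level of the 2% matters (illustration).** If 2% were the chance of a false positive in each test, and a loss in any of eight independent tests counted, the saline rate would be 1 − 0.98^8 = 14.9%. With a correlation of 0.5 between tests it would be about 10%. The plan does not give a per-test rate.

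**Step 4: the combining rule is a real choice (illustration).** Assumptions: 52 per arm, cut-off set for a 2% patient-level chance rate, correlation between tests 0 to 0.5, losses in SDs of change in a stable patient.

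- *Loss of 4 SD in one test.* Take 0.18/0.98 = 18.4% of lidocaine patients as affected. Any-of-eight has 71–72% power, two-of-eight at most 3%, and a comparison of eight-test means about 9–23%.
- *Loss of 0.8 SD in every test, all patients.* Any-of-eight has about 42–65%, two-of-eight about 52–98%.
- *Loss of 0.3 to 0.8 SD in every test, all patients.* Any-of-eight has about 1–65%, the eight-test mean about 52–100%.

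No single rule is best for both patterns.

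**The case against.** **The 2% can be read fairly.** No true saline deficits plus a 2% chance of a false one is a 2% saline rate, which is what reproduces 52. If the same error also applied to lidocaine, its rate would be 20% + 0.8 × 2% = 21.6% and power about 86%. This stands. A reader might infer that the sample size is miscalculated, or that true power is 96%; the documents support neither. What remains is that the text does not say the 2% is a patient-level rate.

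**Saline is plainly the comparator.** A reader might infer that the primary test is against Group 3, where 52 to 65 lidocaine patients against 20 controls would have only 34–39% power. The Research Question, the Null Hypothesis and the power text (two treatment groups, lidocaine and saline) rule that out, and Group 3 is described as a convenience sample. The low power is therefore not a consequence of the plan. The sentence still names the wrong group and must be changed.

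**The sponsor may have a working definition.** The power text refers to earlier observations of strength change. A rule may exist there, but the plan does not state or adopt one.

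**There is still time, because assessors are blinded.** This stands only in part. Outcome collectors are blinded, and Sharing of Results has the schedule becoming known after completion. But providers are unblinded, and the monitoring committee, which includes the statistician, reviews data every 15 subjects with no statement that the review is blinded. The documents do not give the study's status.

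**A mean comparison should replace the proportion, or any-of-eight is the right rule.** Neither follows. The power calculation assumes a responding minority, and Step 4 shows that averaging can do poorly there. The combining rule is a design choice that the documents leave open.

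**Conclusion.** The point holds and should be settled before any analysis by group. The primary endpoint is incomplete: the stated outcome and the tested outcome are on different scales, and the rule joining them is absent. The power claim is correct for 20% v 2%, but it is conditional on a rule that has not been written. A saline rate of 5%, or a lidocaine rate of 15%, would bring power to 53–54% at 52 per arm and 68–70% at 65. It would be wrong to conclude that the trial is underpowered; the documents do not show which rates a rule would give. The labelling of the 2% and of the comparator are wording faults, though the second changes which groups the sentence tells the analyst to test. The reproduction rests on a two-sided test. The multi-test figures rest on assumed correlations and loss sizes, and the main point does not need them.

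**What to change.** Make these changes before anyone who chooses the rule sees outcome data by group.

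1. **Comparator.** In Statistical analysis, name the saline group (Group 2) for the primary test and report Group 3 descriptively.
2. **Deficit.** In the Primary outcome and Statistical analysis texts, define one patient-level deficit: a loss relative to the patient's own baseline, the same summary of readings before and at 30 minutes, one cut-off based on test-retest variability in the baseline readings, and one stated rule for combining the eight tests. Set the cut-off so that the chance rate per patient, not per test, is about 2%. Any-of-eight is one option and is better when a single muscle is affected; requiring two or more is better for a general mild loss.
3. **The 2% and the power.** Reword the 2% as the assumed saline rate of false-positive deficits and restate power for the chosen rule, with a range. Baseline spread omits drift over 30 minutes. With an any-of-eight rule, if the stable SD is 1.1 or 1.25 times larger, a nominal 2% becomes about 4% or 8–10%.
4. **Supporting analysis.** Pre-specify an ANCOVA of 30-minute strength on group and baseline strength, using one summary over the eight tests. The proportion has little power against a general mild loss, and Background treats even mild weakness as hazardous. Keep it supporting, since averaging dilutes a loss confined to one muscle in a minority.
5. **Optional.** Boschloo's test in place of Fisher's raises power for 20% v 2% from 80.3% to 87.5% at 52 per arm, with maximum size 0.0495. Fisher's test is valid as it stands.

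Cost: wording, one extra analysis, equal numbers of readings before and after, and a restated power that may be less favourable.

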#### **Secondary outcomes:**

Mean arterial pressure

Heart rate

Numeric Rating Scale (NRS) pain score

Upper Extremity Functional Index (UEFI) score

Procedure complications

### **PROCEDURES INVOLVED:**

#### **Study design:**

Prospective, randomized, controlled, double blinded trial in patients undergoing CESI for symptoms of cervical radiculitis.

**Group #1:** Interlaminar cervical ESI at the C7-T1 level with triamcinolone 80 mg + 2 mL 1% lidocaine (total volume 4 cc).

**Group #2:** Interlaminar cervical ESI at the C7-T1 level with triamcinolone 80 mg + 2 mL preservative saline (total volume 4 cc).

**Group #3:** Control group (No CESI) cervical or occipital facet injection

Adults who are eligible to have a CESI for treatment of cervical radiculitis at the Northwestern Anesthesiology Pain Medicine Center will be approached by authorized research personnel prior to a patient's CESI is performed and will obtain informed consent from patients who agree to participate.

A pre-procedure NRS pain score and presence of subjective or objective symptoms of UE weakness will be recorded by a blinded authorized study team member. Bilateral handgrip, wrist extension, elbow flexion, and elbow extension strength (myotomes C5-T1) will be measured prior to the injection procedure using a handheld JAMAR® PLUS+ digital dynamometer (Sammons Preston, Bolingbrook, IL) for hand grip strength and a push/pull handheld hydraulic dynamometer (Balego and Associates Inc., St. Paul, MN) for arm strength assessment. Three baseline strength measurements will be recorded for each strength test. Measurements will be taken prior to and 30 minutes following the

injection procedure. Participants will also be queried with the Upper Extremity Functional Index (UEFI) before the injection procedure and again 1 day and 1 week after the procedure (administered via telephone).

Group 1 and 2 participants will be randomized to treatment group based on a random computer-generated schedule (<https://www.randomizer.org>) and will be blinded to the group to which they are assigned. Blinding will not occur with Group 3. Providers will not be blinded to randomization; blinded research personnel will collect all outcome measures in this study.

All standard Pain Center procedures for CESIs will be followed (standard practice) including time out, skin prep, hemodynamic monitoring, image guidance, post-injection instruction etc.

Group 1 and Group 2 group randomization, triamcinolone acetonide 80 mg (Kenalog, E. R. Squibb & Sons Limited, Uxbridge UK) will be combined with 2mL Lidocaine 1% or 2 mL preservative free saline and will be injected during the CESI procedure. In all cases, the total injectate volume will be 4 mL. All injections will be performed with fluoroscopy guidance (current standard practice).

Group 3 will receive standard treatment intramuscular injection of bupivacaine .25% 10-20 mL and methylprednisolone 20 mg.

All participant's will be recovered for approximately 20 minutes following the procedure ( and will be discharged from the clinic with standardized written discharge instructions given to all patients who receive an injection in this practice (includes bathing instructions, activity following the procedure, signs and symptoms of neurologic compromise, for example).

All participants will contacted by telephone by authorized study team member on Day 2 and again 1 week after the procedure (CESI or No CESI) to assess for residual subjective weakness in the hands or arms as well as any other adverse reactions. As the clinical duration of effect for 1% lidocaine is 1-2 hours in most patients, we do not expect to see sustained subjective weakness at 24 hour and 1 week post-CESI assessments as a result of this diluent. As above, the Upper Extremity Functional Index will be administered.

Group 1 and 2 participants will only be recruited for this study for a single CESI. Those who require repeat injections will not be recruited for this study a second or third time.

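### NRS pain is a secondary outcome to be compared between groups, but the only assessment that names it is before the procedure

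*Combined protocol and SAP*

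**What the plan says.** The list of secondary outcomes under Study Endpoints includes "Numeric Rating Scale (NRS) pain score", with no time point. The Statistical analysis paragraph, under Study-wide Number of Participants, states: "Secondary outcomes will be compared using the Mann-Whitney test for continuous data and a chi-squared statistic". It does not say which test applies to NRS, at what time, or whether the score itself or its change is compared.

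NRS is named in one assessment only, in Study design under Procedures Involved: "A pre-procedure NRS pain score and presence of subjective or objective symptoms of UE weakness will be recorded". The same paragraph then describes the two dynamometers and continues: "Three baseline strength measurements will be recorded for each strength test. Measurements will be taken prior to and 30 minutes following the" (its last words refer to the injection). NRS is not named there. UEFI follows, with its own times: "Participants will also be queried with the Upper Extremity Functional Index (UEFI) before the injection procedure and again 1 day and 1 week after".

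Telephone contacts are made "to assess for residual subjective weakness in the hands or arms as well as any other adverse reactions", and UEFI is given at the same calls. Pain is not mentioned.

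**The concern.** A between-group comparison needs an outcome measured after treatment. Scores taken before the injection can differ between randomised arms only by chance, so they carry no information about the diluent. If staff follow the schedule as it most naturally reads, the NRS outcome has a baseline and nothing protocol-specified to set against it.

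Even if a later score is taken, its time and form are not fixed in advance. The time matters. The Significance section contrasts the diluents on immediate pain relief, and Procedures Involved gives lidocaine an effect of 1 to 2 hours in most patients. A score at 30 minutes and a score at one week would therefore answer different questions. An undefined time, and an open choice between raw score and change, leave room to decide after the data are seen.

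The stake is limited to a secondary outcome. Pain is in neither the research question nor the null hypothesis.

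**Working it through.** **Step 1. The schedule, item by item**

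| Item | Before | After | Where |
|---|---|---|---|
| Strength | Yes | 30 minutes | Primary outcome; Study design |
| UEFI | Yes | 1 day and 1 week | Study design |
| Subjective weakness | Yes | Telephone calls | Procedures Involved |
| NRS pain | Yes | None named | Study design |

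Explicit NRS assessments: one before and none after, or one after if the 30-minute sentence is read to include pain.

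**Step 2. What the 30-minute sentence covers**

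Three features point to strength. The sentence immediately before it is about strength measurements. The primary outcome uses the same two times for "dynamometry measurements for each individual in each treatment group before and 30 minutes after the procedure". And the paragraph states later times for UEFI but gives NRS only a pre-procedure label. This is the more natural reading, not the only possible one.

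**Step 3. The plan's own sample-size figure**

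The plan states 52 per group, more than 80% power and an achieved significance level of 0.0004. A two-sided Fisher's exact test at 0.05 with 20% versus 2% gives power 0.803 and actual size 0.00042, so the figure reproduces. It concerns strength only. It is used below solely as the source of n = 52.

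**Step 4. What baseline adjustment would gain, once a post-procedure score exists**

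Inputs: n = 52 per arm (plan); two-sided alpha 0.05 and power 0.80; SD 2.0 to 3.0 and pre/post correlation r of 0.3 to 0.7. SD and r are assumptions, because the documents give neither.

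Detectable difference = noncentrality × SD term × √(2/n). The noncentral t distribution gives a noncentrality of 2.83 at both 101 and 102 degrees of freedom.

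- ANCOVA (df 101): SD term = SD√(1 − r²). At SD 2.5, r 0.5: 2.83 × 2.5 × √0.75 × √(2/52) = 2.83 × 2.165 × 0.196 = 1.20.
- Mann-Whitney, raw score (df 102): SD term = SD, with n replaced by 52 × 3/π = 49.7. At SD 2.5: 2.83 × 2.5 × √(2/49.7) = 2.83 × 2.5 × 0.201 = 1.42.
- Mann-Whitney, change (df 102): as for the raw score, but SD term = SD√(2(1 − r)). At SD 2.5, r 0.5 this equals 2.5, so the result is again 1.42.

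Results in NRS points, as ANCOVA / Mann-Whitney raw / Mann-Whitney change:

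| SD | r = 0.3 | r = 0.5 | r = 0.7 |
|---|---|---|---|
| 2.0 | 1.06 / 1.14 / 1.34 | 0.96 / 1.14 / 1.14 | 0.79 / 1.14 / 0.88 |
| 2.5 | 1.32 / 1.42 / 1.68 | 1.20 / 1.42 / 1.42 | 0.99 / 1.42 / 1.10 |
| 3.0 | 1.59 / 1.70 / 2.01 | 1.44 / 1.70 / 1.70 | 1.19 / 1.70 / 1.32 |

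The gain is small at r = 0.3 (1.32/1.42 = 0.93 of the raw-score figure) and larger at r = 0.7 (0.99/1.42 = 0.70).

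A simulation agrees: 4,000 trials per setting, scores rounded and limited to 0 to 10, assumed means 6 before and 5 after, SD 2.5, r 0.5. With a true difference of 1.5 points, ANCOVA rejected in 92% of trials and Mann-Whitney on the raw score in 83%.

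**The case against.** The strongest reply is that the 30-minute sentence covers the whole paragraph, which opens with NRS. The text has already said that strength is measured before the injection and that baseline strength readings are recorded. If the sentence concerned strength alone, its mention of the time before the procedure would be repetitive. UEFI then comes as an addition because its times differ, and labelling the first NRS score as pre-procedure suggests a later counterpart. This is a fair reading, and it stands as such: the text is ambiguous.

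There are also signs of intent. The protocol says "blinded research personnel will collect all outcome measures in this study". Resources Available mentions post-procedure data, the privacy section allows access to selected medical-record data, and Potential Benefits speaks of learning about pain as well as strength after the injection. That last remark concerns knowledge for investigators, not a pain benefit to participants. Data collection forms are mentioned but are not among the documents, so their content is unknown.

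These points rule out two stronger readings that a reader might infer. One is that no pain score would be taken after the procedure: the documents do not show that. The other is that the sponsor intends to compare pre-procedure scores: no section plans this. For the same reason, a calculation showing that such a comparison rejects only at the alpha level proves nothing about this plan, since that is true by construction. None of the general statements, however, supplies an NRS time or defines the value to be compared.

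Two further objections limit scope. Mean arterial pressure and heart rate also lack assessment times beyond standard monitoring, so NRS is not unique. And Mann-Whitney on either the raw score or the change is valid, so ANCOVA is a gain in precision and not the correction of an error.

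**Conclusion.** The point holds as a gap in specification. NRS is an outcome to be compared, the only assessment that names it precedes treatment, and the one sentence that might supply a later score is ambiguous and most naturally concerns strength. On that reading, the only NRS value the plan guarantees cannot show a treatment effect. On the other reading a 30-minute score exists, but the endpoint still does not say whether the raw score or the change is compared.

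This should be corrected, but it is not critical: the primary outcome and its power are untouched. Confidence is medium because of the ambiguity. The gap itself rests on the text alone. The ranges of 0.79 to 1.59 points (ANCOVA) and 1.14 to 1.70 points (Mann-Whitney, raw score) rest on an assumed SD and correlation, and bear only on the choice of analysis.

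**What to change.** In Study design, name NRS in the post-procedure assessment already planned for strength. Its timing should follow however the sponsor reconciles the recovery period of about 20 minutes before discharge with the 30-minute assessment. That conflict is a separate matter and adds no weight here.

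In Secondary outcomes and Statistical analysis, define the endpoint as post-procedure NRS in Group 1 versus Group 2, adjusted for the pre-procedure NRS already collected (for example ANCOVA), instead of an unadjusted Mann-Whitney test. If Mann-Whitney is kept, state whether it is applied to the raw score or the change.

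The cost is one extra question per patient at an assessment already planned, and a slightly longer analysis section. If a post-procedure NRS was always intended, the scheduling part needs only a clarifying phrase.

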## **BACKGROUND:**

### **Literature:**

Cervical radicular pain is a common problem that is often treated by epidural steroid injection (1). While clinical practice guidelines do not specifically recommend or discourage the use of local anesthetic in the epidural injectate (2), the majority of the published literature on clinical outcomes of cervical epidural steroid injection includes the use of lidocaine in the epidural injectate (3-11). Consequently, many practitioners elect to use local anesthetic in the epidural injectate in order to provide immediate pain relief to patients in cases of exquisitely painful radicular symptoms. Local anesthetic may also be used in such cases to gain additional clinical information regarding a patient's analgesic response, which may help pinpoint a precise anatomic source of pain when the clinical presentation and pain generator is not clear.

Local anesthetic injection into the epidural space has the potential to cause transient weakness of the upper extremities. High doses of local anesthetic in the cervical epidural space (12) and inappropriately placed low-dose local anesthetic in the subdural space or subarachnoid space (13,14) are known to cause motor weakness.

Appropriately placed, low-dose local anesthetic injected into the epidural space via a transforaminal approach, in close proximity to the exiting spinal nerve root, causes motor block in a small proportion of patients (15). However, the effect of low-dose injection of local anesthetic in the cervical interlaminar epidural space on objective upper extremity strength has not been well characterized in the published literature.

This proposition affects post-procedure instructions, as even mild weakness may pose a hazard during performance manual activities that require the upper extremity/extremities such as using a handrail or cane handle for support.

Dynamometry is an established method for assessing muscle strength and motor neuron function with high reliability, and has been used to objectively assess changes in upper extremity strength and has been validated in several patient populations (16-22).

This study aims to determine whether a standard dose of 2 mL 1% lidocaine vs 2mL of saline included as a steroid diluent in a C7-T1 cervical interlaminar epidural steroid injection (CESI) causes an objective change in strength as measured by dynamometry.

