We hypothesize that CESI with lidocaine will cause an objective transient decrease in upper extremity strength, consistent with the expected duration of this local anesthetic.

**Significance:** Cervical radiculitis is a relatively common pain syndrome and is often treated with cervical epidural steroid injection (CESI) when conservative treatments (oral analgesics, physical therapy and activity modification for example) have failed to provide relief of symptoms. There are no universal clinical practice guidelines for the use of or type of diluents when CESI are performed.

Interlaminar CESI may be performed with or without the use of local anesthetics. CESI without the benefit of local anesthetic as a steroid diluent will not provide immediate relief of pain in patients with excruciating radicular symptoms, and also limits clinical information gleaned from the immediate analgesic response. Finally, the lack of immediate pain relief following spine interventions for chronic pain management may decrease patient satisfaction (23).

By evaluating the effects of local anesthetic as a diluent during interlaminar CESI, we will provide information about the potential for objective motor weakness with this commonly performed pain management procedure.

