## **RISKS TO PARTICIPANTS:**

### **Group 1 and 2**

Risks of study participation are the same as those for any fluoroscopically guided cervical ESI performed for management of cervical radiculitis when more conservative methods have been exhausted or failed. The duration of recovery for study participants is no longer than that of a standard CESI performed in this practice.

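### The stated recovery of about 20 minutes does not fit the 30-minute primary strength test, and no section passes the reading to whoever discharges the patient

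*Combined protocol and SAP*

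**What the plan says.** The relevant statements are spread over several sections of the combined protocol and SAP.

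- **Recovery (Procedures Involved, Study design).** All participants are "recovered for approximately 20 minutes following the procedure".
- **Discharge (same section).** After that recovery period they "will be discharged from the clinic with standardized written discharge instructions given to all patients who receive an injection in this practice". The sheet covers bathing, activity and signs of neurologic compromise.
- **Strength test (same section).** "Measurements will be taken prior to and 30 minutes following the" injection procedure. Study Endpoints, Primary outcome, gives the same 30 minutes for all groups.
- **Recovery in the risk section (Risks to Participants, Group 1 and 2).** "The duration of recovery for study participants is no longer than that of a standard CESI performed in this practice". No section says how long standard recovery is.
- **Hazard (Background, Literature).** "This proposition affects post-procedure instructions, as even mild weakness may pose a hazard" in tasks such as using a handrail or cane.
- **Hypothesis (end of the Background literature text).** Lidocaine is expected to cause an "objective transient decrease in upper extremity strength, consistent with the expected duration of this local anesthetic". Study design puts the effect of 1% lidocaine at 1-2 hours in most patients.
- **Planning rate (Study-Wide Number of Participants).** The sample size is set "assuming 20% of patients in the Lidocaine group will demonstrate a motor deficit after the CESI", with no true change under saline and a 2% measurement error.
- **Blinding (Study design).** "Providers will not be blinded to randomization; blinded research personnel will collect all outcome measures in this study".
- **Safety review (Provisions to Monitor the Data).** The study team and a committee review data, every 15 subjects or after a rapid-response event.

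**The concern.** There are two linked gaps.

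First, the text that describes recovery ends it before the primary measurement is due. Staff who follow that text could release a patient before the test, and a patient who has gone has no 30-minute reading, because every later contact is by telephone.

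Second, the trial will hold an objective reading of the hazard that its own Background names, taken while the drug is still expected to act. That reading is collected by blinded research personnel. No section asks them to pass it on, and the discharge sheet is the same for everyone whatever the reading shows. The next planned questions about weakness are the telephone calls at about 24 hours and one week, when the protocol itself expects the lidocaine effect to be over. The committee reviews do not act on one patient's reading before that patient leaves.

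**Working it through.** **1. Timing.** Stated recovery is about 20 minutes and the primary test is at 30 minutes, so the gap is 30 − 20 = about 10 minutes. The test must be done in person: Study design uses a grip dynamometer and a push/pull dynamometer. The protocol therefore needs the patient present after the stated end of recovery, and no sentence says that discharge waits.

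**2. Drug effect left after the test.** With 1-2 hours of effect counted from the injection: 60 − 30 = 30 minutes, and 120 − 30 = 90 minutes.

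**3. The plan's own sample-size figure.** Inputs from Study-Wide Number of Participants: Fisher's exact test, alpha 0.05, 52 per group, 20% against a true zero with 2% measurement error. Sidedness is not stated. Taking 2% as the per-patient rate of apparent deficit under saline, and summing binomial probabilities over all tables with a two-sided p of at most 0.05:

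- power at 20% vs 2%, 52 per group: 0.803 (plan: above 80%);
- attained size at 2% vs 2%: 0.00042 (plan: 0.0004).

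Both figures reproduce, which supports using 20% and 2% as the planned rates of a recorded deficit.

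**4. Expected number of reports.** Count = n × p, with n = 60 per arm and the 2.5th to 97.5th binomial percentiles in brackets:

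| Arm | Rate | Expected readings |
|---|---|---|
| Lidocaine | 20% (protocol) | 12 (6 to 18) |
| Lidocaine | 10% (assumption) | 6 (2 to 11) |
| Lidocaine | 5% (assumption) | 3 (0 to 7) |
| Saline | 2% (protocol) | 1.2 (0 to 4) |

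At the planning rates, 12 + 1.2 = 13.2, or about 13 of 120. Group 3 is not counted, because the protocol gives no rate for it.

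**5. Why the report needs a threshold.** Four strength tests on two sides give 4 × 2 = 8 comparisons per patient. Suppose there is no true change and each post-procedure reading has a 50% chance of being lower than baseline (assumption). The chance of at least one lower reading is then 50% if the eight are fully correlated and 1 − 0.5⁸ = 99.6% if they are independent. A rule to report any loss would flag about 60 to 120 of 120 patients, not 13.

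**6. Missed tests the enrolment can absorb.** With 130 enrolled in Groups 1 and 2 (65 per arm if equal): 65 − 52 = 13, and 13/65 = 20%. With the 60 per group listed elsewhere in the protocol: 60 − 52 = 8, and 8/60 = 13%. Other drop-outs draw on the same allowance.

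**The case against.** The case on the other side is substantial.

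- **The intent is evident.** Two sections fix the primary test at 30 minutes and it can only be done in person, so the protocol read as a whole keeps patients there. The 20 minutes is approximate, and a stray open bracket at that point suggests an unfinished edit. This stands. A reader might infer that patients will in fact leave before the test, and the documents do not support that. What remains is a stated time that contradicts the measurement schedule.
- **The risk section need not be wrong.** A reader might infer that the trial keeps patients longer than usual care while saying otherwise. With no standard recovery time given, that cannot be shown. If standard recovery is 30 minutes or more, the sentence is accurate.
- **Usual care gives cover.** Lidocaine is common in this injection, standard procedures apply, the sheet mentions activity and neurologic signs, the provider already knows the allocation, and nothing forbids the assessor from speaking up. This is fair partial cover, but none of it depends on the reading or requires that it be passed on.
- **The Background remark on instructions is rationale.** It explains why the trial is worth doing and is not an operating commitment. Agreed; it still shows that the investigators regard the finding as relevant to what patients are told.
- **Reporting could affect blinding.** Advice given after a weak reading comes before the telephone functional index and weakness questions. This stands as a small cost.

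**Conclusion.** The point holds as an inconsistency in the stated recovery time together with a missing step at discharge. The protocol should be changed on both, with medium confidence because clinic practice may already cover part of it.

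The size is about 13 of 120 epidural patients with a reportable reading. This rests on the planning rates of 20% and 2%, on 60 per arm, and on the report using the same deficit definition as the primary analysis. The protocol does not give that definition, so the severity behind the 20% is unknown.

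Two stronger readings should be set aside. The 13 are readings and not harmed patients; nothing in the documents gives a rate of injury. Nor is a loss of power shown. It would arise only if patients actually left early, and enrolling 130 (65 per arm if equal) absorbs up to 20% missed tests when nothing else uses the allowance.

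**What to change.** 1. **Study design, recovery sentence.** Replace the approximate 20 minutes with: *until the 30-minute strength test is recorded*.
2. **Risks to Participants, Group 1 and 2.** Keep the sentence on recovery time only if standard recovery in this practice is at least 30 minutes. Otherwise say that participants stay until the strength test is done.
3. **Study design, add:** *After the primary reading is recorded, and before the participant leaves, the blinded assessor tells the treating provider or discharging staff of any strength loss that meets the motor-deficit definition of the primary analysis. No allocation information is passed back to the assessor, the telephone caller or the participant.* The sponsor must write that definition first. What staff then do is for the clinical team.

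The cost is a few sentences. Any extra stay is already implied by the 30-minute test; its length relative to usual care cannot be stated without the standard recovery time. The primary outcome is recorded before any report, so it is unaffected, and providers are already unblinded. The remaining downside is a small risk that advice after a weak reading hints at allocation before the telephone Upper Extremity Functional Index, a secondary outcome. Limiting reports to defined deficits and keeping the communication one-way reduces this risk but does not remove it.
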